4.3. Withdrawal of Subjects

- Withdrawal of study subjects without their consent may occur in parturients who consent to the study but do not undergo neuraxial placement.
- Patients who decide to withdraw prematurely will be withdrawn and provided the standard of care at Tufts Medical Center.

4.4. Recruitment and Retention

4.4.1. Local Recruitment Methods

Faculty in the Obstetrics and Gynecology Department at Tufts Medical Center will be informed about the study at one of the departmental meetings. They will be asked to inform their patients about this study in their clinic visits. The co-investigator, [name] will review medical records and schedule of medical procedures to know their time and date. Once the patients arrive to the labor and delivery unit, he will meet with the patients and discuss the study with them further. If they agree to participate, informed consent will be obtained.

4.4.2. Study-Wide Recruitment Methods

Is this a multicenter study where subjects will be recruited by methods not under the control of the local Tufts site (e.g., call centers, national advertisements)?

Yes No

4.4.3. Payment

Will subjects receive money, gifts, or any other incentive for participating in this study?
This does not include reimbursement for expenses, which is considered in the next section.

Yes No

4.4.4. Reimbursement

Will subjects be reimbursed for their expenses, such as travel, parking, meals, or any other study related costs?

Yes No

5. Study Design

5.1. Study Timelines

- Participation begins at the time of consultation for cesarean delivery on the day of surgery, where the co-investigator [name] will approach the participants and ask them to sign the ICF, and it ends after the post-anesthesia check on postoperative day 1. After recruitment and consent, patients will be randomized using a computer-generated randomization scheme will be used to allocate patients to one of the arms of the study.
- The two arms of the study are as follows:
 - Control group: baseline hemodynamics and anxiety screen; no music
 - Intervention group – Mozart: A study investigator will turn on a playlist of pre-selected Mozart music.
- Given our sample size calculation and that not all women who are approached will consent to the study, we expect recruitment to take 12 months.
- The estimated date for primary analyses will be November 2018
- We estimate that it will take an additional 12 months to complete the study, including statistical analysis and manuscript preparation.

5.2. Procedures

- Is there a placebo control arm?

Yes No

After reviewing their medical records, the co-investigator, [name], will approach parturients meeting inclusion criteria on the day of admission for scheduled cesarean delivery at Tufts Medical Center. The

PROTOCOL TITLE: A Randomized Controlled Trial of Music vs. No Music During Cesarean Delivery on Patient Satisfaction

VERSION DATE: Oct 16, 2017

research study will be explained and parturients will be given an informed consent form to read. After the parturient read through the informed consent form, think about the risks and benefits, and ask questions, she will be asked to sign the form if she wishes to participate in the study. The informed consent form will then be stored in the principal investigator's locked office. Once a study subject is enrolled, the anesthesia provider, obstetric provider, as well as the nurse will be informed that this parturient is part of the study.

Once the subject is recruited, patient demographic data and baseline vitals signs (including anxiety levels) will be collected. All parturients will receive a standardized spinal technique using 1.6 mL of 0.75% hyperbaric bupivacaine with 15mcg fentanyl and 200mcg morphine, which is the typical standard dose at Tufts Medical Center in nulliparous parturients.

Upon entry into the operating room, parturients who are randomized to music will start to listen to the Mozart piano sonatas during the entire procedure, while those randomized to no music will not listen to any music. After at least 5 minutes of listening to music and immediately after the spinal anesthetic is placed, anxiety levels and vitals signs will be assessed again. At the end of surgery, after coming into the PACU, anxiety and vitals will be assessed. Finally, on postoperative day 1, during the hours of 8AM – 1PM, patient satisfaction will be assessed by administering the MSSCS, which should take about 10 minutes to complete. After that, her participation in the study will end.

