2.4. Alternatives

The alternative is not participating in the study.

3. Objectives

The objective of this study is to determine the effect of music on patient satisfaction and anxiety during cesarean delivery. We will evaluate this objective by studying the following outcomes:

- The primary outcome of this study is patient satisfaction. This outcome will be measured using Morgan's "Maternal Satisfaction Scale for Cesarean Section" (MSSCS) on post-operative day one during the hours of 8am-1pm.
- The secondary outcome will include anxiety at several time points (immediately prior to and after neuraxial technique placement as well as at the end of surgery). This will be evaluated using a simple numeric rating score from 0-10, where 0 is no anxiety and 10 is the greatest anxiety.

We hypothesize that parturients exposed to music during cesarean delivery will have greater overall satisfaction and less anxiety.

4. Enrollment and Withdrawal

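### No anxiety score is taken between the post-spinal reading and arrival in the PACU, so anxiety during the operation is bracketed but not observed

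*Combined protocol and SAP*

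**What the plan says.** Section 3 (Objectives) sets the aim: "The objective of this study is to determine the effect of music on patient satisfaction and anxiety during cesarean delivery". It names the anxiety time points as "immediately prior to and after neuraxial technique placement as well as at the end of surgery", on a 0-10 numeric scale. The hypothesis is that "parturients exposed to music during cesarean delivery will have greater overall satisfaction and less anxiety".

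Section 5.2 (Procedures) turns this into a schedule. Once the woman is recruited, "patient demographic data and baseline vitals signs (including anxiety levels) will be collected". On entry to the operating room, women in the music arm "will start to listen to the Mozart piano sonatas during the entire procedure". The second score is placed as follows: "After at least 5 minutes of listening to music and immediately after the spinal anesthetic is placed, anxiety levels and vitals signs". The third is the last: "At the end of surgery, after coming into the PACU, anxiety and vitals will be assessed".

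Section 8.1 (Study Endpoints) lists anxiety and hemodynamics as secondary endpoints without a time point. Section 8.2 (Statistical Analysis) compares mean anxiety and mean blood pressure by t-test, also without saying at which reading.

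**The concern.** The music is meant to act throughout the operation, yet the schedule goes from a score taken just before surgery to one taken after the woman has left the operating room. A difference between arms that existed only during surgery would be recorded nowhere. The last score might still show it, but only to the extent that the effect outlasts the music and the transfer.

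This affects how the anxiety results could be interpreted. If the arms did not differ in the PACU, the trial could not tell whether music had no effect on anxiety during surgery or had one that was gone by recovery. Vital signs follow the same schedule, so the planned hemodynamic comparison also has no scheduled intraoperative reading. No analysis can recover a time point that was not recorded.

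The two sections also place the last score differently. Staff working from section 3 could take it in the operating room with music playing, and staff working from section 5.2 would take it in the PACU. That could mix two exposure states under one label.

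**Working it through.** The plan gives no figure on this point, so the check sets the schedule against the music window.

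| Reading | Section 3 | Section 5.2 | Music on (music arm)? | Within the operation? |
|---|---|---|---|---|
| 1 | Just before neuraxial placement | At recruitment, described before operating room entry | No, under 5.2; possibly yes, under 3 | No |
| 2 | Just after neuraxial placement | Just after the spinal, with at least 5 minutes of music | Yes | No, before surgery |
| 3 | End of surgery | After arrival in the PACU | Not stated; probably no | No |

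1. **Count under section 5.2.** There are 3 scheduled scores: 0 within the operation, 1 in the operating room with music known to be on, and 1 in the PACU.

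2. **Exposure window.** Music starts on entry to the operating room and covers the whole procedure. The second score needs only 5 minutes of it. Assuming that the operation lasts longer than the time from entry to the completed spinal, most of the exposure falls between readings 2 and 3.

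3. **State of exposure at reading 3.** No section gives a stop time or says whether the music continues into the PACU. That it has ended by then is the natural reading of section 5.2, but it is an inference.

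4. **Effect on the contrast.** Let D be the between-arm difference in mean anxiety during surgery and r the fraction of it remaining in the PACU. The PACU comparison then estimates r × D. If r is below 1, the difference is diluted. The documents give no value for D, for r, or for the SD of the anxiety score.

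5. **Shared relief.** Suppose relief that surgery is over lowers both arms by the same amount c. Then (M − c) − (C − c) = M − C, where M and C are the two arm means. The contrast is unchanged unless scores pile up at 0. Shared relief therefore does not by itself pull the result toward zero.

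6. **Sample size.** The 18 subjects in section 8.3 (22 with attrition) come from satisfaction scores. They say nothing about power for anxiety.

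7. **Baseline.** Section 3 puts the first score just before neuraxial placement, and section 5.2 puts it at recruitment. Under section 3 it could fall after operating room entry with music already playing. It would then not be a pre-exposure baseline.

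**The case against.** The strongest reply is that section 3 itself defines how the objective will be evaluated. It names three peri-procedural time points, and section 5.2 broadly follows them. On this view the PACU clause only says where the end-of-surgery score is taken.

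A reader might infer that the stated objective is not measured at all. The documents do not support that:

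- The phrase about cesarean delivery can describe the exposure rather than the outcome, as it does in the hypothesis. Applied to the outcomes, it would also cover satisfaction, which is measured only on postoperative day 1.
- One score is taken under exposure: the post-spinal score follows at least 5 minutes of music.

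A reader might also take it as settled that the music is off by the PACU score, or that relief after surgery biases the comparison toward zero. The first is likely but not stated. The second needs a floor effect, for which the documents give no evidence.

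These replies limit the point without removing it. However the objective is read, no score comes from the operation itself, and the two sections differ on when the first and last scores are taken.

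A further fair objection is that a score at skin closure would still miss incision and delivery. That stands, and it bears on which event to choose.

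**Conclusion.** The point holds in limited form. Under section 5.2, 0 of 3 anxiety scores fall within the operation. The one score known to be taken under music precedes surgery, and the last is taken after transfer, probably after exposure has ended. Anxiety during surgery is bracketed by these readings but not observed.

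Any dilution in the PACU score rests on two assumptions: that the music stops before that score, and that its effect fades once it stops. Its size cannot be derived from the documents. A power figure would depend wholly on an assumed SD, effect and carry-over, so none is offered.

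Only secondary outcomes are affected. The primary outcome stands. The change is still worth making, because it is cheap and the missing reading cannot be recovered later.

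**What to change.** - **Section 5.2:** add a 0-10 anxiety score with vital signs, in both arms, in the operating room at a fixed event while the music is still playing in the music arm. An event during surgery, such as shortly after delivery, is preferable. End of skin closure is the latest useful choice and would capture only the end of the operation.
- **Section 5.2:** keep the PACU score, label it as post-exposure, and state when the music stops.
- **Sections 3 and 5.2:** use the same time points in both. Reconcile the end of surgery with PACU arrival, and the score just before neuraxial placement with the one at recruitment. Say which reading addresses anxiety during the operation. If no intraoperative score is added, word the objective to match the readings that are taken.
- **Sections 8.1 and 8.2:** name the reading, or readings, at which anxiety and hemodynamics will be compared.

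The cost is one brief verbal question per woman during surgery (at most 22 extra scores at the planned enrolment), a field on the data form and some protocol wording. Vital signs are assumed to be on the monitor already.

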5.3. Evaluations

Will you perform any laboratory tests for this study?

Yes No

5.4. Collection and Storage of Human Biological Specimens (Tissue Banking)

Will biological specimens be stored for future, unspecified, research?

Yes No

6. Ethics and Protection of Human Subjects

6.1. Informed Consent Process

Will subjects be required to provide informed consent?

Yes No

- The parturients will be informed about the study during a clinic visit before being admitted for surgery.
- The informed consent will be taken in a private room in the labor and delivery unit on the day of the procedure.
- The patient will have one hour before the start of the procedure to make a decision regarding enrollment.
- The consent will be obtained in person and documented in writing following “SOP: Informed Consent Process for Research (HRP-090)”.
- Non-English speakers will be enrolled using interpreters and IRB approved Short Forms per the IRB's Short Form policy

6.2. Waiver or Alteration of Consent Process

- Is a waiver or alteration of the consent process being requested for this study?
 Yes **No**
- Is a waiver of the consent process being requested for parents for research involving children?
 Yes **No**
- Is a waiver of the consent process for planned emergency research being requested?
 Yes **No**

6.3. Confidentiality

In order to maintain confidentiality, the following measures will be taken:

- All study related materials, including consent forms and data collection forms, will be stored in the principal investigator's locked office
- The principal investigator and co-investigators will have exclusive access to the forms
- Digital data will be stored in a hospital provided, password protected, Box account
- Data will not be coded, as it will be stored in a protected online account.
- Records will be stored for 7 years after the study is closed with the IRB, as per IRB policy.
- A certificate of confidentiality will not be obtained.

6.4. Provisions to Protect the Privacy Interests of Subjects

Subjects will be assured that their interaction with any member of the research team is optional, as well as the information they share.

6.5. Provisions to Monitor the Study to Ensure the Safety of Subjects

- The standard of care at Tufts Medical Center is to collect safety information on all patients undergoing surgery through an established computerized system called Anesthesia Touch. Safety information and adverse events that will be collected includes failure of spinal analgesia. For the purposes of this study, the principal investigator will periodically (every 6 months) evaluate the safety data and assess the risks and benefits to assess subject safety. The purpose of obtaining this information is to ensure that no untoward events are occurring. This information will be obtained after signing the ICF. The statistical tests that will be performed on the safety data to determine whether harm is occurring will include a chi-squared test, to compare proportions between groups.
- Stopping rule: we do not anticipate a stopping rule to this study.
- No Data and Safety Monitoring Board will be used in this study.

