8.3. Number of Subjects

- A previous study demonstrated that the total satisfaction score in parturients who get midazolam pre-operatively vs. those who do not is 130.3 ± 10.5 vs. 113.6 ± 11.9 , respectively. Although we do not have similar data for music, we expect that the effect of Mozart music will be similar to that of midazolam because both music and midazolam work as anxiolytics and may play an important role in patient satisfaction. Therefore, we will expect to see a similar difference in patient satisfaction.
- Using G*Power 3.1, we determined that in order to detect a difference between the two groups using a two-tailed T-test with power of 80% and alpha of 0.05, the total number of subjects needed is 18. In order to account for 20% attrition rate, the total number of subjects that would be required to complete study aims is **22**.

VERSION DATE: Oct 16, 2017

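### The chi-squared test that section 6.5 names for judging harm is too weak at about 11 women per arm; counts with exact bounds should replace it

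*Combined protocol and SAP*

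**What the plan says.** Section 6.5 gives the aim of the safety data as follows: "The purpose of obtaining this information is to ensure that no untoward events are occurring". The event it names is in this sentence: "Safety information and adverse events that will be collected includes failure of spinal analgesia". On method it says: "The statistical tests that will be performed on the safety data to determine whether harm is occurring will include a chi-squared test", the comparison being of proportions between the groups. The test belongs to a wider review, in which "the principal investigator will periodically (every 6 months) evaluate the safety data and assess the risks and benefits to assess subject safety". On further safeguards the section says "we do not anticipate a stopping rule to this study" and "No Data and Safety Monitoring Board will be used in this study".

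Section 8.3 fixes the size of the trial: 18 women, raised to 22 to allow for 20% attrition. Section 5.1 describes two arms and says "we expect recruitment to take 12 months".

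Sections 7.1 and 7.2 deal with individual events. The first defines an unanticipated problem by three criteria. The second passes adverse events from the co-investigator to the principal investigator, and reportable new information to the IRB within 5 business days.

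For the safety comparison the documents give no event rate, significance level, power, detectable difference or confidence interval. They do not say how a non-significant result is to be read.

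**The concern.** A significance test can answer whether harm is occurring only if it would probably reject when harm is present. In arms this small, a p-value above 0.05 is the likely result over a wide range of real increases in event rates, so it carries little information. Section 6.5 asks the safety data for reassurance, names this one test, and gives no interval or rule of interpretation to accompany it. A non-significant result could then be carried into the six-monthly review, or into the final report, as a finding of no harm that the data do not support.

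This is a problem of false negatives. It is separate from whether the chi-squared approximation is accurate at small counts. Changing to an exact test would leave the problem in place and raise the miss rate.

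**Working it through.** **Inputs from the documents.** Total 22, and 18 before attrition (8.3); two arms (5.1); between-group chi-squared test (6.5); review every 6 months (6.5) during 12 months of recruitment (5.1).

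**Assumptions.** Allocation 1:1, so 11 per arm (9 per arm if only 18 women are evaluable). Two-sided 5% level for the safety test. No continuity correction unless stated. Event rates are illustrative. Section 8.5 speaks of three arms; if that were right, the arms would be smaller and the test weaker.

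**1. The plan's own figure.** The difference is 130.3 − 113.6 = 16.7. The pooled SD is √[(10.5² + 11.9²)/2] = 11.22, so d = 16.7/11.22 = 1.49. A two-sided t-test at 5% has 79.0% power with 8 per arm and 84.2% with 9 per arm, so 18 in total reproduces. For attrition, 18 × 1.2 = 21.6, which gives 22. (Dividing by 0.8 gives 22.5, hence 23; this does not affect the present point.) The sample size rests on a large effect on satisfaction. Safety played no part in it.

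**2. Smallest table that reaches significance.** For events x in one arm and 0 in the other, with n = 11 per arm, X² = N(ad − bc)²/(product of the four margins).
- 3 vs 0: 22 × (3 × 11)²/(11 × 11 × 3 × 19) = 23,958/6,897 = 3.47, p = 0.062.
- 4 vs 0: 22 × (4 × 11)²/(11 × 11 × 4 × 18) = 42,592/8,712 = 4.89, p = 0.027.

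So at least 4 of 11 (36%) against none is needed. With Yates' correction or Fisher's test it is 5 of 11 (4 of 11 gives p = 0.097 and 0.090). This step needs no assumed event rate. For 3 of 11 against 0 of 11, the Newcombe 95% CI for the risk difference runs from about −4 to +57 percentage points.

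**3. Probability of missing a fourfold rise.** All 2×2 tables under two independent binomials were enumerated. Miss rate = 1 − the total probability of tables with p ≤ 0.05, for 11 per arm.

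| Control vs music (assumed) | Uncorrected chi-squared | Fisher |
|---|---|---|
| 1% vs 4% | 99.9% | >99.9% |
| 3% vs 12% | 97.5% | 99.6% |
| 5% vs 20% | 90.4% | 97.1% |
| 10% vs 40% | 66.1% | 80.9% |
| 20% vs 80% | 13.3% | 26.6% |

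With 9 per arm, 5% vs 20% is missed 94.0% of the time. At a 6-month look, about halfway through recruitment with 5 to 6 per arm, it is missed 95% to 93% of the time. For 80% power at 5% vs 20%, the normal-approximation formula gives 76 per arm.

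**4. What zero events would show.** The exact one-sided 95% upper bound is 1 − 0.05^(1/n).
- n = 11: 1 − 0.05^(1/11) = 23.8%.
- n = 9: 1 − 0.05^(1/9) = 28.3%.

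**The case against.** The best defence is that the test does not stand alone. Section 6.5 says the tests will include chi-squared, and it places them within the principal investigator's assessment of risks and benefits. Sections 7.1 and 7.2 supply event-level criteria and prompt reporting. The main physical risk named, injury to the eardrum from loud music, would be recognised case by case and not from a comparison of rates. Volume follows the patient's preference (2.2), and risk to the fetus is described as no more than minimal (6.8). Low power for safety is common to any trial of 22 people.

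Most of this stands, and it rules out three stronger readings that a reader might infer.
- **That the test alone decides whether harm is occurring, with no event-level safeguard.** Sections 6.5, 7.1 and 7.2 show otherwise.
- **That p > 0.05 will be taken as showing no harm.** No section says so. The sentence about untoward events gives the reason for collecting the data and is not a decision rule. What the documents support is that the reading is left open.
- **That a fourfold rise is missed about 90% of the time without qualification.** This holds at an assumed 5% control rate with the uncorrected test. The documents give no rate, and at higher control rates the miss rate is much lower.

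The defence does not show that the named test can serve its stated purpose. The six-monthly review has no other stated statistical basis for comparing the arms.

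**Conclusion.** The concern holds in limited form. The one statistical method that section 6.5 names for detecting harm is not capable of it at this sample size. Without assuming any event rate, more than a third of one arm must have the event, against none in the other, before the test signals. For fourfold rises from control rates of about 5% or less, it misses at least about 90% of the time. It becomes reasonably sensitive only when events are common and the rise is very large.

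These figures rest on 11 women per arm, 1:1 allocation and a two-sided 5% level, none of which is stated for the safety comparison. Smaller arms, a continuity correction or Fisher's test would all make the miss rates in the table higher.

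Severity is minor. The intervention is low risk, individual events are reported by another route, and neither the primary result nor the sample size is affected. The consequence is an open risk that a non-significant p-value is misread as reassurance.

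**What to change.** In section 6.5, replace the chi-squared test as the statistical basis for judging harm with the following, at each six-monthly review and at the end:
- the number of women with each event and the number observed, by arm;
- an exact one-sided 95% upper bound for the event rate in the music arm;
- a 95% CI for the risk difference, by a method suited to small counts (for example Newcombe).

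All of these should be calculated from the numbers actually observed. The zero-event bounds above should serve as illustrations and not be written in as fixed figures, because they change with attrition. Any p-value should be labelled descriptive. One added sentence should say that a non-significant comparison between arms is not evidence of no harm. Case-by-case review is already covered by sections 7.1 and 7.2; a cross-reference is enough.

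The cost is a few sentences and a little more analysis, with no extra patients, staff or procedures. The downside is a safety statement that looks less reassuring.
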